10.2.2 ANALYSIS OF THE SECONDARY ENDPOINT(S)

For the secondary endpoints, we will estimate the incidence of the overall incidence of treatment-related and non-treatment related toxicity and the exact confidence interval. In addition, each toxicity event will be tabulated and summarized by severity and major organ site according to the CTCAE v5.0. Time-to-event analysis (e.g., Kaplan-Meier and cumulative incidence curves) will be used to evaluate event-free and overall survival.

10.2.3 ANALYSIS OF THE EXPLORATORY ENDPOINT(S)

10.2.3.1 Transcriptome analysis to identify potential qualitative differences in CSF-1R⁺ cells that predict patient response

For statistical analysis, we will need >5 responders and non-responders. We anticipate this will be feasible with 14 participants enrolling on the assay positive arm (not all will respond *in vivo*, and the non-responders can be used for comparison). In addition, we will also collect samples from the 7 patients enrolling on the assay negative arm who are likely to be non-responders.

If sufficient participants initially respond to JNJ-40346527 but later develop resistance, we will also collect these resistant samples to be analyzed by RNAseq as a separate comparison group. This may provide insight into how patients develop resistance to JNJ-40346527.

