	
alcoholic steatohepatitis, primary biliary cirrhosis, extrahepatic obstruction caused by cholelithiasis, cirrhosis of the liver, portal hypertension, or history of autoimmune hepatitis.
 
Untreated HIV or active hepatitis C detectable by PCR, or chronic hepatitis B (patients positive for hepatitis B core antibody who are receiving IVIG are eligible if HepB PCR is negative).
 
9. Untreated HIV or active hepatitis C detectable by PCR, or chronic hepatitis B (patients positive for hepatitis B core antibody who are receiving IVIG are eligible if HepB PCR is negative).
 
10. Known history of cerebrovascular accident, myocardial infarction, or intracranial hemorrhage within 2 months of enrollment.
 
11. Clinically significant surgery within 2 weeks of enrollment.
 
12. Per PI discretion, active infection that is not well controlled by antibacterial or antiviral therapy.
 
13. Cancer-directed therapy within 2 weeks prior to starting treatment, with the exception of hydroxyurea, which is allowed to control white blood cell count. Hydroxyurea will be weaned as soon as clinically feasible.
 
14. Unwillingness to receive infusion of blood products.
 
15. Drugs that affect the CYP3A4 systems are allowed and essential for cancer patients, including anti-fungals but should be used with caution.
 
16. Patients with uncontrolled white blood cell count (defined as >50 K/cu mm not controlled with hydrea).

<hr/>	
Investigational Product(s)	JNJ-40346527 will be administered at a dose of 150 mg PO twice daily in continuous 28-day cycles
<hr/>	
Statistical Considerations	A Simon 2-stage minimax design will be used to determine clinical efficacy. For each arm, 7 participants will be enrolled in the first stage. If there is at least 1 response among the first 7 participants, the trial will proceed to the second stage and enroll an additional 7 participants. The treatment is considered promising if there are at least 3 responses among 14 participants. The study has 80% power to test the best objective response rate of 5% (poor) vs. 30% (desirable) using one-sided 5% significance level.
Efficacy Assessments	Assess the best objective response rate, duration of response to JNJ-40346527, overall survival and event-free survival in participants with relapsed/refractory AML as stratified by ex vivo

	sensitivity.

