RNAseq will also be performed on leukemia samples from expression signature in CSF-1R⁺ cells that predicts patient response. We hypothesize that there may be a qualitative difference in CSF-1R⁺ CD14⁺ and CSF-1R⁻ CD14⁺ cells that results in clinical sensitivity to CSF-1R inhibitors. This difference may not be detected by the CyTOF approach outlined above, as that requires using candidate phospho-protein and cytokines. RNAseq offers an unbiased way to analyze the functional difference between these cells.

CSF-1R⁺ CD14⁺ and CSF-1R⁻ CD14⁺ cells will be isolated with magnetic antibody sorting. Since not every subject will have sufficient cells for RNAseq, we will review the FACS analysis of patients at screening to identify subjects that are likely to have sufficient numbers of CD14⁺ and CSF-1R⁺ cells. Our preliminary data has found that CSF-1R⁺ cells account for about 1-3% of the total number of cells. 40 ml of peripheral blood will be collected from subjects with a total peripheral blood WBC>10. This WBC typically correlates with a yield of ~100 million cells after Ficoll separation, which will subsequently allow for collection of ≥ 1 million CSF-1R⁺ CD14⁺ cells to process for RNA. This peripheral blood sample will be collected on day 1 prior to JNJ-

40346527 treatment.

Collectively, these studies are aimed at identifying a genetic or expression signature of CSF-1R⁺ cells that predicts clinical response to JNJ-40346527, as well as uncovering potential mechanisms of resistance/adaptation.

7.3.5 MASS CYTOMETRY EVALUATION OF JNJ-40346527 EFFECT ON PHOSPHO-SIGNALING PROTEINS IN IMMUNE CELL POPULATIONS

This exploratory study will utilize mass cytometry (cytometry by Time of Flight, CyTOF) to evaluate the effect that JNJ-40346527 has on intracellular phospho-signaling of proteins within immune cell populations (i.e., cytotoxic T cells, etc.) in pre- and post-treatment samples. These studies are intended to identify biomarkers that predict patient response and prioritize potential combination strategies for future clinical trials.

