10.3 SAMPLE SIZE, POWER, ACCRUAL RATE AND STUDY DURATION

10.3.1 SAMPLE SIZE AND POWER

The sample size for each group was derived according to the 2-stage design with minimax criteria using the following parameter settings: 1) 80% power; 2) 5% significance level; 3) historical response rate of 5% (poor response), and 4) desired response rate of 30% (promising response).²¹ The sample size and power analyses were conducted using PASS 14 software (<http://www.ncss.com/software/pass/>). Based on the expected accrual rate of 14 participants per year, we anticipate this trial to take 36 months (24 months of accrual and 12 month of minimum follow-up).

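### The RNAseq responder comparison is called feasible with 14 assay-positive patients, but the design's 30% target rate gives about a 22% chance of the more than 5 responders it requires

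*Combined protocol and SAP*

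**What the plan says.** Section 10.2.3.1 gives the requirement for the transcriptome analysis and the claim that it can be met: "For statistical analysis, we will need >5 responders and non-responders. We anticipate this will be feasible with 14 participants" on the assay-positive arm. It notes that some assay-positive patients will not respond and can serve as the comparison group, and adds that "we will also collect samples from the 7 patients enrolling on the assay negative arm who are likely to be non-responders". It attaches no probability to the feasibility statement and does not say what happens if the minimum is missed.

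Section 10.3.1 sizes each arm using a "desired response rate of 30% (promising response"), against 5% as the poor rate. Section 10.2.1 gives the rule for each arm: 7 patients, then 7 more if at least 1 responds, and the treatment is promising with at least 3 responses in 14.

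On sample yield, Section 7.3.4 says "Since not every subject will have sufficient cells for RNAseq", and limits the 40 ml blood collection to patients with a white count above 10. It does not say what share of patients will qualify.

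**The concern.** The analysis needs at least 6 responders, while the arm counts as a success with 3. The 30% rate on which the arm is sized implies about 4. So the trial could succeed on its own terms and still miss the minimum that the protocol sets for this comparison.

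At stake is the planned test behind one exploratory objective in Section 2.3, an expression signature in CSF-1R-positive cells that predicts response. This is the only analysis that Section 10.2.3 describes, and it has no fallback. If there are too few responders, the analysis would be either dropped or improvised after the response data are known.

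**Working it through.** **Inputs.** Minimum of more than 5 responders and non-responders, read as at least 6 in each group; 14 assay-positive and 7 assay-negative patients (Section 10.2.3.1). Response rates of 30% and 5% (Section 10.3.1). Stage 1 stop at 0 of 7, success at 3 or more of 14 (Section 10.2.1).

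**Step 1: reproduce the design.** The Synopsis states: "The study has 80% power to test the best objective response rate of 5% (poor) vs. 30% (desirable) using one-sided 5% significance level".
- Ignoring the stage 1 stop, P(X ≥ 3 | 14, 0.30) = 0.839.
- The stop removes paths with 0 of 7 followed by at least 3 of 7: 0.7^7 × P(at least 3 of 7) = 0.0824 × 0.353 = 0.029.
- Power = 0.839 − 0.029 = 0.810. The exact type I error at 5% is 0.027.

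The stated power and significance level hold, and a search confirms 14 as the minimax sample size.

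**Step 2: expected responders.** 14 × 0.30 = 4.2, below the minimum of 6.

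**Step 3: chance of at least 6.** With X binomial (14, 0.30), the probabilities of 0 to 5 responders are 0.0068, 0.0407, 0.1134, 0.1943, 0.2290 and 0.1963, which sum to 0.7805. So P(X ≥ 6) = 1 − 0.7805 = 0.2195. The stage 1 stop lowers this only to 0.2192, because few paths have no response in the first 7 and then 6 or 7 in the next 7.

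**Step 4: chance given a positive arm.** Any two-stage path with 6 or more responders also meets the success rule. So the chance of at least 6, given that the arm is declared promising at a true rate of 30%, is 0.2192 / 0.8101 = 27%.

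**Step 5: which group is short.** At least 6 non-responders among the 14 means at most 8 responders, which has probability 0.992. The shortage is of responders, so assay-negative patients who do not respond do nothing to relieve it.

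**Step 6: assay-negative responders.** Let Y be binomial (7, 0.05). The pooled chance is the sum over j of P(Y = j) × P(X ≥ 6 − j) = 0.698 × 0.219 + 0.257 × 0.413 + about 0.029 for j of 2 or more = 0.288.

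**Step 7: sensitivity**, all with the stage 1 stop.

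| Setting | Chance of reaching the minimum |
|---|---|
| 20% response rate | 4.4% |
| 25% | 11% |
| 30% (design rate) | 22% |
| 40% | 51% |
| 50% | 79% |
| 30%, at least 5 accepted | 41% |
| 30%, plus 7 assay-negative patients at 5% | 29% |
| 30%, plus up to 14 assay-negative patients at 5% | 31% |

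An even chance needs a true rate of about 40%, and an 80% chance needs about 51%.

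**The case against.** The strongest reply is that 30% is a sizing parameter and not a forecast. The protocol gives no expected response rate for assay-positive patients, and its remark that not all of them will respond would suit authors who expect well over 30%. At 50% the sentence would be reasonable. This rightly stops anyone from calling 30% the sponsor's prediction. It does not rescue the sentence, because no higher rate appears anywhere in the document and 30% is the rate the plan itself calls desirable.

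Second, the same design parameters apply to both arms. If both responded at 30%, the chance of at least 6 responders would be 62% with 7 assay-negative patients and 82% with up to 14. But Section 3.1 expects only the assay-positive arm to reach stage 2, and Section 10.2.3.1 expects assay-negative patients not to respond. That scenario contradicts the plan's own expectation.

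Third, the threshold is loosely worded and unexplained. The text does not say that it applies to each group, although a two-group comparison makes that the natural reading. Accepting 5 responders gives 41%, still below even.

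Two stronger readings are tempting and should be resisted. A reader might infer that the objective cannot be carried out at all. The documents do not support that: 3 to 5 responders still allow a descriptive comparison. A reader might also put a number on the loss from insufficient cells. That needs a yield the protocol does not give, and usually the assumption that yield is unrelated to response. Section 7.3.2 reports a trend in the other direction, with more ex vivo sensitivity where non-leukemic CD14-positive cells express more CSF-1R, so responders may be the patients more likely to yield enough cells.

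**Conclusion.** The point stands as a should-fix on an exploratory analysis. The plan anticipates a feasibility that its own parameters do not deliver: about 22% at the design rate, and below even on each alternative that keeps 30% for the assay-positive arm and 5% for the assay-negative arm. This rests on reading the minimum as at least 6 per group, on 30% as the only target rate in the document, and on independent responses. Cell-yield losses can only reduce the number of sequenced responders, by an amount that cannot be stated.

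A reader might infer an arithmetic error in the sample size. There is none. The two-stage design reproduces, and the primary endpoint, secondary endpoints and stopping rules are untouched.

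**What to change.** In Section 10.2.3.1:

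- Replace the feasibility statement with the probability: about 22% for at least 6 responders of 14 at a 30% rate, before cell-yield losses, with the 40% and 50% cases alongside. State that the minimum applies to each group.
- Prespecify, as the main exploratory response association, expression against percent change in marrow blasts, in all sequenced patients with paired baseline and follow-up marrow. Blast counts are already part of the marrow exam (Section 7.2.5). Say plainly that patients without a pair drop out, such as those who leave before the Day 29 marrow or whose marrow could not be aspirated, and report how many.
- Treat association with log IC50 as supportive only, since it measures ex vivo sensitivity and not clinical response.
- Report responders against non-responders descriptively whatever the number of responders, with formal testing only if the stated minimum is met.

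The cost is wording: no new samples, visits or patients. The downsides are a less favourable stated figure and the loss of patients without paired marrow from the main association.

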3. STUDY DESIGN AND ENDPOINTS

3.1 DESCRIPTION OF THE STUDY DESIGN

Refer to Section 10, **STATISTICAL CONSIDERATIONS** for additional information regarding statistical methods used in this study.

This is a Phase 2, Simon 2-stage minimax design to determine clinical efficacy of JNJ-40346527 in relapsed/refractory AML. Participants must meet the inclusion criteria, have none of the exclusion criteria, and have provided written informed consent before the conduct of any screening tests not performed routinely in their treatment.

Results from preclinical studies suggest that responsive patients may be selected by using an *ex vivo* assay with JNJ-40346527. Eligible participants will be divided into two treatment arms based on an *ex vivo* sensitivity of AML cells derived from either bone marrow aspirates or peripheral blood (if inaspirable and $\geq 20\%$ circulating blasts). Participants with an *ex vivo* IC_{50} that is $\leq 20\%$ of the median IC_{50} (to be determined with preclinical testing) will be considered sensitive to JNJ-40346527 (termed “assay positive”), whereas those with an $IC_{50} > 20\%$ of the median IC_{50} will be considered insensitive (termed “assay negative”) for purposes of assignment. This threshold is set prior to the study start and does not change. This will result in 2 study arms: 1) Assay positive and 2) Assay negative (Figure 6). Patients that screen fail (for example indeterminate assay results or insufficient sample) will not be included in the study. Patients can rescreen per provider discretion.

For each arm, 7 participants will be enrolled in the first stage. If there is at least 1 response among the first 7 participants, the study will proceed to the second stage, in which an additional 7 participants will be enrolled. The treatment is considered promising if there are at least 3 responses among 14 participants. The best objective response and exact confidence intervals will be estimated using the binomial distribution for each arm.

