An identical FACS analysis will also be performed on bone marrow biopsies after one month of therapy to assess the expression of CSF-1R and CD14+ cells after JNJ-40346527 treatment in

both clinical responders and non-responders. This will establish if there is a reduction only in the CSF-1R-expressing population, or if other lineages are also affected. For example, it may be that JNJ-40346527 only affects CD14⁺ cells that express CSF-1R, or JNJ-40346527 may shrink the entire population of CD14⁺ cells. The relative proportion of leukemia cells, B-cells, and T-cells will also be evaluated after treatment.

Since this work will be done in a CLIA-certified clinical lab using standard flow procedures and equipment, it would provide a companion diagnostic that could be rapidly incorporated into standard flow protocols for larger trials.

7.3.3 ASSESSING A GENETIC SIGNATURE THAT PREDICTS RESPONSE TO JNJ-40346527.

Genomic DNA from leukemia patients will be analyzed for frequent leukemia mutations to determine if there is a genetic signature that predicts response to JNJ-40346527. The GeneTrails [Hematologic Malignancies Gene Panel](#) developed at OHSU's [Knight Diagnostic Laboratory](#) covers 76 genes that are frequently mutated in both lymphoid and myeloid leukemia, and is run as a CLIA-approved (CLIA#38D2018256), standard-of-care test on leukemia patients (Refer to D). Additional sites will use their in-house leukemia panel per standard of care. Redacted source documentation from sites will be sent to OHSU for genetic marker analysis.

Sequencing data from participants who have clinically responded to JNJ-40346527 will be compared to that from non-responders, to determine if there are genetic markers of clinical response. The goal is to identify a potential genetic subtype of AML that predicts clinical response to JNJ-40346527, either alone or in combination with the quantitative and qualitative analysis of CSF-1R⁺ cells.

Additionally, coded and de-identified DNA samples will be stored in the [name] Lab (OHSU) for further retrospective analyses, including targeted sequencing, whole-exome sequencing, or methylation analysis. Samples will be stored indefinitely. Access to samples will be limited to study staff.

7.3.4 TRANSCRIPTOME ANALYSIS TO IDENTIFY POTENTIAL QUALITATIVE DIFFERENCES IN CSF-1R⁺ CELLS THAT PREDICT PATIENT RESPONSE.

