Bone marrow aspirates and blood samples will be collected and purified by Ficoll gradient. The cells will be fixed and labeled with antibodies coupled to heavy metal isotopes for CyTOF using established protocols. Cells expressing CSF-1R will be evaluated by CyTOF to look at downstream signaling pathways such as phospho-STAT3/5, phospho-Akt, phospho-MAPK, phospho-p38 and phospho-S6. As a positive control, we will use the GDM-1 cell line, which has an activating mutation in CSF-1R and responds robustly to CSF-1R inhibition *in vitro*. Antibodies to identify relevant subpopulations of monocytes, lymphocytes, and leukemia cells will be used to analyze phospho-signaling in CSF-1R⁺ cells, CD14⁺ cells, and leukemia cells (Table 6).

[figure not shown]
Table 6. Antibody panel for analysis of kinase signaling and cytokine analysis by CyTOF.

CSF-1R	CD14	pSTAT3	pSTAT5	pMAPK	pS6	pP38	pAkt
EGF	FGF2	HGF	SDF1	VEGF	IL-6	IL-1 \square	MCP1
MCP2	CXCL1	IL-8	IL-10	RANTES	TGF \square	MIP1b	G-CSF
IL3	MIP1a	GCSF-1					

To examine the secreted proteins from the supportive cells, we will pretreat samples with a Golgi trap (brefeldin A) to retain secreted proteins in the cells for intracellular staining. A selection of signaling molecules known to impact leukemia cell survival will also be evaluated, including a focus on the CSF-1R⁺ and CD14⁺ cells. Particularly, we will investigate the expression of the ligand CSF-1, which may act in an autocrine manner to expand supportive CSF-1R⁺ cells ().

Bone marrow aspirates will be tested at screening and after one cycle of therapy to evaluate signaling in CSF-1R⁺ CD14⁺ cells, CSF-1R⁻ CD14⁺ cells, immune cell populations, and leukemia cells both before and after treatment. Responsive versus non-responsive subjects will be compared to determine if there is a qualitative difference in CSF-1R⁺ cells that predicts clinical response to JNJ-40346527, and if this population either disappears or is functionally altered by JNJ-40346527 treatment. The goal is to determine if there is a qualitative signature of CSF-1R⁺ cells that predicts clinical response to JNJ-40346527 that can be used to identify sensitive patients or immunotherapeutic targets in future clinical trials.

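### Biomarker contrasts of responders with non-responders that combine the two arms cannot separate clinical response from the ex vivo assay result

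*Combined protocol and SAP*

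**What the plan says.** Section 3.1 defines the arms by the ex vivo result: "This will result in 2 study arms: 1) Assay positive and 2) Assay negative". It anticipates that only the assay-positive arm will go on to stage 2, for 21 participants in all.

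Section 10.2.3.1 sets a minimum group size for the RNAseq comparison: "For statistical analysis, we will need >5 responders and non-responders". It continues: "We anticipate this will be feasible with 14 participants enrolling on the assay positive arm", and notes that assay-positive patients who do not respond can act as comparators. It then adds: "we will also collect samples from the 7 patients enrolling on the assay negative arm who are likely to be non-responders". It names no test, model, stratification or arm term.

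The other two signature analyses are worded by response alone. Section 7.3.3: "Sequencing data from participants who have clinically responded to JNJ-40346527 will be compared to that from non-responders". Section 7.3.5: "Responsive versus non-responsive subjects will be compared to determine if there is a qualitative difference". Section 7.3.2 will correlate CSF-1R expression with both ex vivo sensitivity and clinical response, but does not say how the two will be separated. Only the primary endpoint (Section 10.2.1) is specified for each arm separately.

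**The concern.** Two differences are mixed when responders come mainly from one assay-defined arm and many of the non-responders come from the other. One is response versus non-response; the other is assay-positive versus assay-negative. Any feature that tracks the assay will differ between the groups, even if it says nothing about who responds among patients with the same assay result.

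The protocol itself anticipates both conditions for this. Section 3.1 expects response to differ by arm. Section 7.3.2 reports a trend linking CSF-1R expression on non-leukemic CD14+ cells to sensitivity to CSF-1R inhibition. Sections 7.3.2 to 7.3.5 hope for a marker, perhaps a companion diagnostic, to identify sensitive patients in later trials. A reader of the results would want to know whether a reported signature adds to the assay or restates it.

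**Working it through.** **The plan's own figure.** The biomarker plan has no power figure; its 14 and 7 come from the Simon design in Sections 10.2.1 and 10.3.1 (continue on at least 1 of 7, promising on at least 3 of 14). With b the binomial probability, P(promising) = Σ over x = 1 to 7 of b(7, x, p) × P(Bin(7, p) ≥ 3 − x). This gives 81.0% at p = 30% and 2.7% at p = 5%, consistent with the stated 80% power and one-sided 5% level. A search confirms this as the minimax design.

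**Inputs for the contrast.** From the documents: 14 assay-positive and 7 assay-negative patients (10.2.3.1), and stopping at 7 for futility only on no responses (10.2.4). Assumed: the response rate in each arm. Section 10.3.1 gives 5% and 30% as the poor and desired rates for each group, not as expected rates for the negative and positive arms. Also assumed: a marker whose mean differs by d within-arm SDs between arms and is unrelated to response within an arm.

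**Formula.** Expected responder minus non-responder difference = d × (assay-positive share of responders − assay-positive share of non-responders).

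**Path the plan anticipates** (30% response in the positive arm; negative arm stopped with 0 of 7):

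- Responders: 14 × 0.30 = 4.2, all assay-positive (100%).
- Non-responders: 9.8 + 7 = 16.8, of whom 9.8 / 16.8 = 58% are assay-positive.
- Difference: (1 − 0.583) × d = 0.42d.

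**Other assumed rates, keeping 14 + 7 patients:**

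| Positive / negative arm response | Responders | Non-responders | Assay-positive share of each | Difference |
|---|---|---|---|---|
| 30% / 10% | 4.2 + 0.7 = 4.9 | 9.8 + 6.3 = 16.1 | 86% vs 61% | 0.25d |
| 30% / 5% | 4.2 + 0.35 = 4.55 | 9.8 + 6.65 = 16.45 | 92% vs 60% | 0.33d |
| 50% / 5% | 7 + 0.35 = 7.35 | 7 + 6.65 = 13.65 | 95% vs 51% | 0.44d |
| 30% / 30% | 4.2 + 2.1 = 6.3 | 9.8 + 4.9 = 14.7 | 67% vs 67% | 0 |

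The rows with responders in the negative arm are averages for sensitivity only. An actual response there would send that arm to stage 2.

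**Dependence on the enrolment quota.** Keep 30% and 5% but enrol 14 assay-negative patients. Responders are 4.2 + 0.7 = 4.9 (86% assay-positive) and non-responders 9.8 + 13.3 = 23.1 (42%), so the difference is 0.43d instead of 0.33d. Nothing biological has changed.

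**How often it would be flagged.** Take the minimum of 6 responders, all assay-positive, against 8 assay-positive and 7 assay-negative non-responders. The expected difference is (7/15)d = 0.47d. In 100,000 simulated trials, a combined two-sided 5% t-test flagged the marker in 11% (d = 1), 17% (d = 1.5), 22% (d = 2) and 31% (d = 3). Within the assay-positive arm (6 vs 8) the rate was about 5% for every d.

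**Scarce group.** P(at least 6 responders of 14) is 22% at a 30% response rate, 51% at 40% and 79% at 50%. Extra likely non-responders do not ease that limit.

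**The case against.** The strongest reply is that an assay-linked marker is not a false finding. If the arms respond at different rates, anything that tracks the assay does predict response across the combined population. A reader might infer from the figures above that a combined signature would be spurious; the documents do not support that. The quota need not inflate the association either. Section 1.2.1 reports 20-25% of AML samples sensitive to CSF-1R inhibitors. With that mix and rates of 30% and 5%, the same formula gives 0.44d at 20% (0.600 − 0.156) and 0.47d at 25% (0.667 − 0.197), against 0.33d at 14:7. A marker that replaced a three-day viable-cell assay would also serve the stated aims: Section 1.2.1 wants the CD14 cells that predict sensitivity characterised, and Section 7.3.2 looks toward a flow-based companion diagnostic. All of this stands. It limits the point to what the combined contrast can show, which is not information beyond the assay.

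A reader might also take pooling as the stated method. It is not stated. Section 10.2.3.1 describes assay-positive non-responders as comparators before adding the assay-negative samples. Combining them is the natural reading, since they are added as likely non-responders in a paragraph about group sizes, but the exact criticism is that the contrast is unspecified.

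Finally, the analyses are exploratory and arm is known for every participant, so stratification remains possible at analysis. That bears on priority; it does not remove the reason to name the contrast in advance.

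**Conclusion.** The point holds in a limited form. As worded, the signature analyses allow a combined contrast in which response and assay status are confounded by design, and no section provides a within-arm contrast or an arm term. On the path the plan anticipates, with an assumed 30% response in the assay-positive arm and 0 of 7 in the other, about 0.42 of any marker difference between arms appears as a responder difference. The tabulated rates give about 0.25d to 0.44d, and 0 if the arms respond equally. The arm-specific rates and d are assumptions; the documents give neither for these analyses.

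The documents do not support concluding that a combined signature would be wrong or useless. They support only that it could not be presented as adding to the assay. Priority is low: the primary endpoint, stopping rules and sample size are unaffected.

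**What to change.** In Sections 10.2.3.1, 7.3.3 and 7.3.5, state that:

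- responders and non-responders will be compared within the assay-positive arm, or with arm as a term in the model;
- assay-positive versus assay-negative will be reported as a separate contrast;
- any combined contrast will be shown beside these and labelled as not separating assay status from response.

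If the assay-negative arm has no responders, a stratified exact test gains nothing from it. In a linear model with an arm term, the response estimate then equals the within-positive-arm difference, and the assay-negative samples inform only the residual variance. The within-positive-arm contrast is the operative one in that case.

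The change is to wording only and needs no new samples. The cost is fewer non-responders in the main contrast: about 10 instead of 17 at a 30% response rate. At those expected counts and equal SDs, the standard error rises by about 7%: √(1/4.2 + 1/9.8) = 0.583 against √(1/4.2 + 1/16.8) = 0.546. Actual RNAseq numbers may be smaller, since Section 7.3.4 notes that not every participant will have enough cells.
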